### 5.2.6 Medical History

Prior to enrollment, subjects will be assessed for pre-existing conditions and illnesses, both past and ongoing. Any such conditions will be documented in the source document. Significant (clinically relevant) medical history (reported as diagnosis) including conditions/illnesses for which the subject is or has been followed by a physician or conditions/illnesses that could resume during the course of the study or lead to an SAE or to a repetitive outpatient care will be collected in the (electronic) case report book (CRB). The significant medical history section of the CRB contains a core list of body systems and disorders that could be used to prompt comprehensive reporting, as well as space for the reporting of specific conditions and illnesses.

---

a The components of all study vaccines are listed in Section 6.1.1 and in the Investigator's Brochure

b Chronic illness may include, but is not limited to, cardiac disorders, renal disorders, auto-immune disorders, diabetes, psychomotor diseases, and known congenital or genetic diseases.

c For the Russian Federation, febrile illness is defined as temperature  $\geq 37^{\circ}\text{C}$ . A prospective subject should not be included in the study until the condition has resolved or the febrile event has subsided.

For each condition, the data collected will be limited to:

Diagnosis (this is preferable to reporting signs and symptoms)

Presence or absence of the condition at enrollment

The reporting of signs and symptoms in lieu of a diagnosis is strongly discouraged.

Dates, medications, and body systems are not to be recorded, and the information collected will not be coded. Its purpose is to assist in the later interpretation of safety data collected during the study.

### ***For the Russian Federation Only***

Any clinically significant abnormal results of the Visit 0 CBC, blood chemistry, or urinalysis according to Investigator's judgment will be reported as medical history. All laboratory tests will be sampled and analyzed locally. Results of the lab tests will be assessed by the Investigator. The Investigator should choose to not include the subject in the study if any of these laboratory tests have the potential to impact the health of the subject after vaccination. The laboratory values for CBC, blood chemistry, and urinalysis will only be collected in the CRF if they are clinically significant. Visit 0 laboratory tests are to be considered clinically significant in the following circumstances:

- Symptomatic
- Requiring corrective treatment or additional consultation by relevant specialist
- Leading to study vaccine discontinuation or postponing vaccination
- Meet SAE criteria

## **5.2.7 Contraindications for Subsequent Vaccinations**

### **5.2.7.1 Temporary Contraindications**

Should a subject experience one of the conditions listed below, the Investigator will postpone further vaccination until the condition is resolved. Postponement must still be within the timeframe for vaccination indicated in the Table of Study Procedures.

- Moderate or severe acute illness/infection (according to Investigator judgment) on the day of vaccination or febrile illness (temperature  $\geq 38^{\circ}\text{C}^{\text{a}}$ ). The vaccine should not be administered until the condition has resolved or the febrile event has subsided.
- Planned receipt of any vaccine in the 4 weeks before or after any study vaccination except for influenza vaccination, which may be received at least 2 weeks before or 2 weeks after any

---

a For the Russian Federation, febrile illness is defined as temperature  $\geq 37^{\circ}\text{C}$ ). A prospective subject should not be included in the study until the condition has resolved or the febrile event has subsided.

study vaccination. This exception includes monovalent pandemic influenza vaccines and multivalent influenza vaccines.

### 5.2.7.2 Definitive Contraindicationsa

The following AEs constitute absolute contraindications to subsequent vaccination with any of the study vaccines. If a subject should experience any of these events during the study, that subject is not to receive any additional study vaccines but should continue in the study and be followed up for safety only as per protocol up to 6 months after the last vaccination received.

#### **MenACYW conjugate vaccine:**

- 1) History of an Arthus-like reaction after vaccination with a tetanus toxoid-containing vaccine.
- 2) History of Guillain-Barré syndrome within 6 weeks after vaccination with a tetanus toxoid-containing vaccine
- 3) Severe allergic reaction (eg, anaphylaxis) after a previous dose of vaccine, any component of the vaccine, or any other tetanus toxoid or meningococcal-containing vaccine.

#### **Menveo® (Mexico only):**

- 4) Severe allergic reaction (eg, anaphylaxis) after a previous dose of Menveo®, any component of this BL vaccine, or any other CRM197, diphtheria toxoid or meningococcal-containing vaccine is a contraindication to administration of Menveo®.

#### **M-M-R®II (Mexico only):**

- 5) Hypersensitivity to any component of the vaccine, including gelatin.
- 6) Anaphylactic or anaphylactoid reactions to neomycin.
- 7) Active untreated tuberculosis.
- 8) Patients receiving immunosuppressive therapy. (This contraindication does not apply to patients who are receiving corticosteroids as replacement therapy, eg, for Addison's disease.)
- 9) Individuals with blood dyscrasias, leukemia, lymphomas of any type, or other malignant neoplasms affecting the bone marrow or lymphatic systems.
- 10) Primary and acquired immunodeficiency states, including patients who are immunosuppressed in association with AIDS or other clinical manifestations of infection with HIV; cellular immune deficiencies; and hypogammaglobulinemic and dysgammaglobulinemic states.

---

a This list is not definitive and is not the final list of contraindications to vaccination. The investigators at each site should refer to the local package inserts and / or reference safety information for each of the routine pediatric vaccines when making these judgements and decisions.

**Pevnar 13® (pneumococcal 13 – valent conjugate vaccine):**

***For Mexico:***

- 11) Severe allergic reaction (eg, anaphylaxis) to any component of Pevnar 13® or any diphtheria toxoid-containing vaccine.
- 12) Infants or children with coagulation disorders, premature infants.

***For the Russian Federation:***

- 13) Allergic reaction after previous dose of Pevnar 13® or Pevnar® (including, anaphylactic shock, severe generalized allergic reactions).
- 14) Hypersensitivity to diphtheria toxoid and / or any other component of Pevnar 13®.

**Hexacima® (Mexico only) (DTaP-IPV//Hib vaccine):**

- 1) Hypersensitivity to any of the active substances, or to any of the excipients contained in the formula, or to any pertussis-containing vaccine, or after a previous administration of the vaccine or any other vaccine that contains the same components or constituents.
- 2) Vaccination must be postponed in the case of moderate to high fever and/or in the presence of any acute disease. A mild infection and/or low grade fever does not represent a contraindication.
- 3) Vaccination with Hexacima® is contraindicated if the infant that experienced an encephalopathy of unknown origin during the 7 days after the administration of any pertussis-containing vaccine (acellular or “whole cell”). Under these circumstances the anti-pertussis vaccination must be suspended and the vaccination against diphtheria, tetanus, hepatitis B, poliovirus and Hib must be continued.
- 4) Uncontrolled neurologic disorder and nervous system or uncontrolled epilepsy: The pertussis-containing vaccines must be stopped until the treatment for this condition has been established, the affection is controlled and the benefit versus the risk of vaccination must be evident.

**PENTAXIM®**

***For the Russian Federation:***

- 1) Evolving encephalopathy with or without convulsions.
- 2) Encephalopathy of unknown origin within 7 days following a previous dose of any vaccine containing *Bordetella pertussis* antigens (whole-cell or acellular pertussis vaccines).
- 3) Strong reaction within 48 hours of a previous dose of any vaccine containing pertussis component: fever  $\geq 40^{\circ}\text{C}$ , abnormal prolonged crying syndrome (longer than 3 hours), febrile and afebrile seizures, hypotonic-hyporesponsive syndrome.
- 4) Hypersensitivity reaction after a previous dose of any vaccine against diphtheria, tetanus, pertussis, polio or (*Haemophilus influenzae* type b) Hib-infection.
- 5) Hypersensitivity reaction to any component of the vaccine, including glutaraldehyde, neomycin, streptomycin and polymyxin B.

**ENGERIX-B® (hepatitis B vaccine)a:**

***For the Russian Federation:***

- 1) Hypersensitivity to any component of the vaccine (and baker's yeast) or manifestations of hypersensitivity reaction, as well as severe reaction (fever > 40°C, swelling and redness > 8 cm in diameter at the site of administration) after previous administration of ENGERIX-B®b vaccine.

**RotaTeq® (rotavirus vaccine):**

***For Mexico:***

- 1) Hypersensitivity to any component of the vaccine.
- 2) Individuals who develop symptoms suggestive of hypersensitivity after receiving a dose of pentavalent rotavirus vaccine (RV5) (RotaTeq®) should not receive further doses of RV5 (RotaTeq®).
- 3) Individuals with Severe Combined Immunodeficiency Disease (SCID). Cases of gastroenteritis associated with vaccine virus have been reported post-marketing in infants with SCID.

**5.2.8 Conditions for Withdrawal**

Parents / Guardians will be informed that they have the right to withdraw their child from the study at any time.

A subject may be withdrawn from the study:

- 1) At the discretion of the Investigator or Sponsor due to safety concerns or significant non-compliance with the protocol (based on the Investigator's judgment), without the subject's permission (withdrawal)
- 2) At the request of the parent / guardian (dropout)

The reason for a withdrawal or dropout should be clearly documented in the source documents and on the CRB.

The Investigator must determine whether voluntary withdrawal is due to safety concerns (in which case, the reason for discontinuation will be noted as "Adverse Event") or for another reason.

Withdrawn subjects will not be replaced.

---

a HIV infection is not considered as a contraindication for hepatitis B vaccination.

b In the event ENGERIX B® cannot be supplied in the Russian Federation, a locally licensed hepatitis B vaccine will be administered instead.

## 5.2.9 Lost to Follow-up Procedures

In the case of subjects who fail to return for a follow-up examination, documented reasonable effort (ie, documented telephone calls and certified mail) should be undertaken to locate or recall them, or at least to determine their health status while fully respecting their rights. These efforts should be documented in the CRB and in the source documents.

## 5.2.10 Classification of Subjects Who Discontinue the Study

For any subject who discontinues the study prior to completion, the most significant reason for early termination will be checked in the CRB. Reasons are listed below from the most significant to the least significant (refer to the CRB completion instructions for additional details and examples):

Adverse Event	To be used when the subject is permanently terminated from the study because of an AE (including an SAE), as defined in Section 9.3.2.1 . This category also applies if the subject experiences a definitive contraindication that is an SAE or AE.
Lost to Follow-up	To be used when the subject’s parent / guardian cannot be found or contacted in spite of efforts to locate him/her before the date of his/her planned last visit, as outlined in Section 5.2.9 . The certified letter was sent by the Investigator and returned unsigned, and the parent/guardian did not give any other news and did not bring the child to any following visit.
Protocol Deviation	To be used: In case of significant non-compliance with the protocol (eg, deviation of the Inclusion / Exclusion criteria, non-compliance with time windows, blood sampling or vaccination refusal, missed injection/treatment, or error in the vaccine/treatment administration). If the subject experiences a definitive contraindication that is a protocol deviation. The parent/guardian signed the certified letter sent by the Investigator but did not give any other news and did not come to any following visit.
Withdrawal by Subject or Parent / Guardian / Legally Acceptable Representative	To be used: When the parent/guardian indicated unwillingness to continue in the study When the parent/guardian made the decision to discontinue participation in the study for any personal reason other than an SAE/AE (eg, subject is relocating, inform consent withdrawal, etc.)

## 5.2.11 Follow-up of Discontinuations

The site should complete all scheduled safety follow-ups and contact any subject who has prematurely terminated the study because of an AE, a protocol deviation, or loss of eligibility, including definitive contraindications.

For subjects where the reason for early termination was lost to follow-up or if the subject withdrew informed consent and specified that they do not want to be contacted again and it is documented in the source document, the site will not attempt to obtain further safety information.

If the subject’s status at the end of the study is “Withdrawal by Subject or Parent / Guardian / Legally Acceptable Representative”, the site will attempt to contact the subjects parents except if they specified that they do not want to be contacted again and it is documented in the source document.

### 5.3 Safety Emergency Call

If, as per the Investigator's judgment, a subject experiences a medical emergency, the Investigator may contact the Sponsor's RMO for advice on study related medical question or problem. If the RMO is not available, then the Investigator may contact the Call Center—available 24 hours a day, 7 days a week—that will forward all safety emergency calls to the appropriate primary or back-up Sanofi Pasteur contact, as needed. The toll-free contact information for the Call Center is provided in the Operating Guidelines.

This process does not replace the need to report an SAE. The Investigator is still required to follow the protocol-defined process for reporting SAEs to the Global Pharmacovigilance (GPV) Department (Please refer to [Section 10](#)).

In case of emergency code-breaking, the Investigator is required to follow the code-breaking procedures described in [Section 6.4](#).

### 5.4 Modification of the Study and Protocol

Any amendments to this study plan and protocol must be discussed with and approved by the Sponsor. If agreement is reached concerning the need for an amendment, it will be produced in writing by the Sponsor, and the amended version of the protocol will replace the earlier version. All substantial amendments (eg, those that affect the conduct of the study or the safety of subjects) require IEC / IRB approval, and must also be forwarded to regulatory authorities.

An administrative amendment to a protocol is one that modifies some administrative, logistical, or other aspect of the study but does not affect its scientific quality or have an impact on the subjects' safety. The IECs / IRBs may be informed, as per local regulations.

The Investigator is responsible for ensuring that changes to an approved study, during the period for which IEC / IRB approval has already been given, are not initiated without IEC / IRB review and approval, except to eliminate apparent immediate hazards to subjects.

### 5.5 Interruption of the Study

The study may be discontinued if new data about the investigational product resulting from this or any other studies become available; or for administrative reasons; or on advice of the Sponsor, the Investigators, the IECs/IRBs, or the governing regulatory authorities in the countries where the study is taking place.

If the study is prematurely terminated or suspended, the Sponsor shall promptly inform the Investigators, the IECs/IRBs, the regulatory authorities, and any contract research organization(s) (CROs) used in the study of the reason for termination or suspension, as specified by the applicable regulatory requirements. The Investigator shall promptly inform the subjects' parents/guardians and should assure appropriate subject therapy and/or follow-up.

There will be an internal team at the level of the Sponsor (SMT), which will review the data being generated from all the ongoing studies with MenACYW conjugate vaccine at regular intervals for any new safety signals or safety concerns. The SMT is empowered to recommend a pause in both recruitment and / or further vaccination while it investigates any potential signal or concern.

## 6 Vaccines Administered

For proper management of the supply and accountability of the products, MenACYW conjugate vaccine will be considered an Investigational Medicinal Product (IMP). All other vaccines will be classified as IMP or non-investigational medicinal products (NIMPs), in accordance with the national laws and regulations of each country.

### 6.1 Identity of the Investigational Products

Identity of the Investigational Products

#### 6.1.1 Identity of Study Product

**MenACYW conjugate vaccine:** Meningococcal Polysaccharide (Serogroups A, C, Y, and W) Tetanus Toxoid Conjugate Vaccine (Sanofi Pasteur Inc., Swiftwater, Pennsylvania ([PA], USA)

**Form:** Liquid solution

**Dose:** 0.5 milliliter (mL)

**Route:** IM

**Batch number:** To be determined (TBD)

##### 6.1.1.1 Composition

Each 0.5 mL dose of MenACYW conjugate vaccine is formulated in sodium acetate buffered saline solution to contain the following ingredients:

Meningococcal capsular polysaccharides:

Serogroup A.....	10 micrograms (µg)
Serogroup C.....	10 µg
Serogroup Y.....	10 µg
Serogroup W.....	10 µg

Tetanus toxoid protein carrier ..... approximately 55 µga

##### 6.1.1.2 Preparation and Administration

MenACYW conjugate vaccine is supplied in single-dose vials (0.5 mL).

---

a Tetanus toxoid protein quantity is approximate and dependent on the polysaccharide-to-protein ratio for the conjugates used in each formulation.

Prior to administration, all study products must be inspected visually for cracks, broken seals, correct label content (see Section 6.3.1), and extraneous particulate matter and / or discoloration, whenever solution and container permit. If any of these conditions exists, the vaccine must not be administered. A replacement dose is to be used, and the event is to be reported to the Sponsor.

The rubber stopper should not be removed from any of the vaccine vials.

The site of IM injection should be prepared with a suitable antiseptic prior to administration of 1 dose (0.5 mL) of MenACYW conjugate vaccine in the thigh (preferably the right thigh). After vaccine administration, the used syringe and needle will be disposed of in accordance with currently established guidelines.

Subjects must be kept under observation for 30 minutes after each vaccination to ensure their safety, and any reactions during this period will be documented in the CRB. Appropriate medical equipment and emergency medications, including epinephrine (1:1000), must be available on site in the event of an anaphylactic, vasovagal, or other immediate allergic reaction.

Each 0.5 mL dose is to be injected IM into anterolateral area of the thigh.

### 6.1.1.3 Dose Selection and Timing

Subjects in Group 1 and Group 2 (Mexico) will receive MenACYW conjugate vaccine administered at 2, 6, and 12 months of age.

Subjects in Group 3 (the Russian Federation) will receive MenACYW conjugate vaccine administered at 3, 6, and 12 months of age.

### 6.1.2 Identity of Control Product

**Menveo®:** Meningococcal (Groups A, C, Y and W 135) Oligosaccharide Diphtheria CRM197 Conjugate Vaccine (GlaxoSmithKline Vaccines, Srl, Bellaria-Rosia 53018, Sovicille [SI], Italy)

**Form:** Lyophilized powder and liquid components are combined to produce a Solution for Intramuscular Injection

**Dose:** 0.5 mL

**Route:** IM

**Batch number:** TBD

#### 6.1.2.1 Composition

Each 0.5 mL dose of vaccine contains the following active ingredients:

MenA oligosaccharide.....	10 µg
MenC oligosaccharide.....	5 µg
MenY oligosaccharide.....	5 µg
MenW-135 oligosaccharide.....	5 µg
CRM 197 protein.....	32.7 to 64.1 µg

Other ingredients per 0.5 mL dose: residual formaldehyde ..... < 0.30 µg

### 6.1.2.2 Preparation and Administration

Menveo® is supplied in 2 vials that must be combined prior to administration: reconstitute the MenA lyophilized conjugate vaccine component with the MenCYW-135 liquid conjugate vaccine component immediately before administration.

See the investigational labeling for Menveo® for precautions and administration instructions.

Each 0.5 mL dose is to be injected IM into the anterolateral thigh area.

### 6.1.2.3 Dose Selection and Timing

Subjects in Group 2 (Mexico) will receive Menveo® administered at 2, 4, 6, and 12 months of age.

## 6.2 Identity of Other Products

### 6.2.1 Identity of Other Product 1

**M-M-R®II** (Measles, Mumps, and Rubella Virus Vaccine Live) (Merck & Co., Inc., Whitehouse Station, NJ, USA)

**Form:** Lyophilized live virus vaccine

**Dose:** 0.5 mL

**Route:** SC

**Batch number:** TBD

#### 6.2.1.1 Composition

Each 0.5 mL dose contains live attenuated virus:

Measles virus (derived from Ender's Edmonston strain) propagated in chick embryo cell culture  
..... not less than 1000 TCID50

Mumps virus (Jeryl Lynn™ [B level] strain) propagated in chick embryo cell culture  
..... not less than 12,500 TCID50

Rubella virus (Wistar RA 27/3 strain) propagated in WI-38 human diploid lung fibroblasts  
..... not less than 1000 TCID50

Each 0.5 mL dose is calculated to contain sorbitol (14.5 mg), sodium phosphate, sucrose (1.9 mg), sodium chloride, hydrolyzed gelatin (14.5 mg), recombinant human albumin (< 0.3 mg), fetal bovine serum (< 1 parts per million [ppm]), other buffer and media ingredients and approximately 25 µg of neomycin.

#### 6.2.1.2 Preparation and Administration

See the M-M-R®II package insert (42) for specific precautions and the procedure for preparing and administering M-M-R®II.

Each 0.5 mL dose is to be injected SC into the outer aspect of upper arm.

The site of injection should be documented. The site of injection should be prepared with a suitable antiseptic. After administration of the vaccine, the used syringe and needle will be disposed of in accordance with currently established guidelines.

### 6.2.1.3 Dose Selection and Timing

Subjects in Groups 1 and 2 (Mexico) will receive M-M-R®II administered at 12 months of age.

Subjects in Group 3 and 4 (the Russian Federation) will receive MMR administered at 12 months of age.

### 6.2.2 Identity of Other Product 2

Monosodium L-glutamate 0.5 mg  
Sodium **Prevnar 13®**: Pneumococcal 13-valent Conjugate Vaccine (Diphtheria CRM197 Protein)  
(Pfizer Inc, Philadelphia, PA, USA)

**Form:** Suspension for injection

**Dose:** 0.5 mL

**Route:** IM

**Batch number:** TBD

#### 6.2.2.1 Composition

Each 0.5 mL dose of the vaccine is formulated to contain:

*Streptococcus pneumoniae* serotypes 1, 3, 4, 5, 6A, 7F, 9V, 14, 18C, 19A, 19F, 23F  
saccharides..... approximately 2.2 µg of each  
6B saccharides .....4.4 µg

Excipients:

CRM197 carrier protein .....34 µg  
Polysorbate 80 .....100 µg  
Succinate buffer.....295 µg  
Aluminum as aluminum phosphate adjuvant .....125 µg

#### 6.2.2.2 Preparation and Administration

Prevnar 13® is supplied in a single-dose prefilled syringe.

See the Prevnar 13® package insert (43) for specific precautions and the procedure for preparing and administering Prevnar 13®.

Each 0.5 mL dose is to be injected IM middle section of lower third of the anterolateral region of the right thigh.

The site of injection should be documented. The site of injection should be prepared with a suitable antiseptic. After administration of the vaccine, the used syringe and needle will be disposed of in accordance with currently established guidelines.

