#### **5.1.4 Visit Procedures**

##### ***Mexico***

##### **Visit 1 (Day 0): Inclusion, Blood Sampling (BL), and Vaccination**

- 1) Give the parent / guardian information about the study, obtain written informed consent, and give him/her a signed copy.
- 2) Check inclusion and exclusion criteria for eligibility.
- 3) Collect demographic data.
- 4) Obtain verbal medical history about the subject, including ongoing medications and history of maternal immunization against tetanus.
- 5) Conduct a physical examination
- 6) Measure temperature. If the temperature is  $\geq 38^{\circ}\text{C}$ , postpone vaccination until the condition is resolved.
- 7) Contact IRT system for randomization / allocation of subject number / vaccine assignment

- 8) Review temporary contraindications for blood sampling. Ensure the subject has not had any antibiotics within the previous 72 hours (3 days).
- 9) Collect 6-mL blood sample (BL0001) (see [Section 7.1](#) for detailed instructions regarding the handling of blood samples). If attempts to obtain the first blood draw are unsuccessful (after reasonable attempts as per local regulations / practice), then Visit 1 can be rescheduled to a later date at which point inclusion/exclusion criteria must be re-validated. If the first blood draw cannot be obtained, the subject will be withdrawn from the study without being vaccinated
- 10) Review warnings and precautions to vaccinations.
- 11) Administer the appropriate study vaccines per Operating Guidelines. Each vaccine should be administered in an assigned location and documented appropriatelya.
  - Meningococcal vaccine: inject IM into the anterolateral area of the thigh (preferably the right thigh).b,c
  - Prevnar 13®: inject IM into the anterolateral thigh (preferably the left thigh).b
  - Hexacima®: inject IM into the anterolateral area of the thigh (preferably the left thigh).b
  - RotaTeq®: administer PO per instructions in the package insert.
- 12) Keep the subject under observation for 30 minutes and record any AE in the source document.
- 13) Give the parent / guardian a diary card (DC1), a thermometer, and a ruler, and go over the instructions for their use.
- 14) Remind the parent / guardian to expect a telephone call 8 days after Visit 1 and to bring back the diary card when they return for Visit 2 at a specified date and time.

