- 15) Remind the parent / guardian to notify the site in case of an SAE.
- 16) Complete the CRFs for this visit.

---

a Failure to administer vaccines in the designated limb will not constitute a protocol deviation, but should be recorded as a comment in the CRF. If the initial vaccines are administered in the wrong limbs, this should be corrected for subsequent injections.

b The only other vaccine that can be administered with the meningococcal vaccine in the right thigh is ENGERIX-B®. Do not administer Pentaxim® or PREVNAR 13® in the right thigh.

c Multiple injections given in the same extremity should be separated as far as possible preferably 2.54 cm to 3.81 cm apart with a minimum of 2.54 cm. Keep the subject under observation for 30 minutes and record any AR in the source document.

Telephone Call 1 (8 [+2] days after Visit 1)

**Note:** If Day 8 falls on a weekend or a holiday, the telephone call may be made on the following business day.

- 1) Record relevant information concerning the subject's health status on the telephone contact form. If an SAE has occurred that has not yet been reported, follow the instructions in [Section 10](#) for reporting it.
- 2) Remind the parent / guardian to do the following:
  - Complete the D0 to D07 pages of the diary card.
  - Complete the remaining pages of the diary card, and bring them to the next visit.
  - Notify the site in case of an SAE.

Visit 2 (60 [+14] days after Visit 1): Collection of Safety Information and Vaccination

- 1) If the diary card information from D0 to D07 (DC1) has not yet been obtained, obtain it at this time. Collect and review the pages of the diary card with the parent / guardian, including any AEs, medications, or therapy that occurred since vaccination. If an SAE, including an AESI, has occurred, follow the instructions in [Section 10](#) for reporting it.
- 2) Review warnings and precautions to vaccinations.
- 3) Review contraindications to subsequent vaccinations.
- 4) Review conditions for withdrawal.
- 5) Contact IRT system for dose number for all vaccines to be given.
- 6) Administer the appropriate study vaccine per Operating Guidelines. Each vaccine should be administered in an assigned location and documented appropriately.

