***For subjects in Groups 1 and 2:***

- Prevnar 13®: inject IM into the anterolateral area of the thigh (preferably the left thigh).

---

a The only other vaccine that can be administered with the meningococcal vaccine in the right thigh is ENGERIX-B®. Do not administer Pentaxim® or PREVNAR 13® in the right thigh.

b Multiple injections given in the same extremity should be separated as far as possible preferably 2.54 cm to 3.81 cm apart with a minimum of 2.54 cm. Keep the subject under observation for 30 minutes and record any adverse reaction (AR) in the source document.

- Hexacima®: inject IM into the anterolateral area of the thigh (preferably the left thigh).b
  - RotaTeq®: administer PO per instructions in the package insert.
- 7) Give the parent / guardian a diary card (DC2).
  - 8) Remind the parent / guardian to expect a telephone call 8 days after Visit 2 and to bring back the diary card when they return for Visit 3 at a specified date and time.
  - 9) Remind the parent / guardian to notify the site in case of an SAE.
  - 10) Complete the relevant CRFs for this visit.

Telephone Call 2 (Group 2) (8 [+2] days after Visit 2)

Refer to steps in Telephone Call 1.

Visit 3 (60 [+14] days after Visit 2): Collection of Safety Information and Vaccination

- 1) If the diary card information from D0 to D07 (DC2) has not yet been obtained, obtain it at this time. Collect and review the pages of the diary card with the parent / guardian, including any AEs, medications, or therapy that occurred since vaccination. If an SAE, including an AESI, has occurred, follow the instructions in [Section 10](#) for reporting it.
- 2) Review warnings and precautions to vaccinations.
- 3) Review contraindications to subsequent vaccinations.
- 4) Review conditions for withdrawal.
- 5) Contact IRT system for dose number for all vaccines to be given.
- 6) Administer the appropriate study vaccine per Operating Guidelines. Each vaccine should be administered in an assigned location and documented appropriately.
  - Meningococcal vaccine: inject IM into the anterolateral area of the thigh (preferably the right thigh).a,b
  - Hexacima®: inject IM into the anterolateral area of the thigh (preferably the left thigh).
  - Prevnar 13®: inject IM into the anterolateral area of the thigh (preferably the left thigh).b

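### Protocol 6.2.2.2 sends every Prevnar 13 dose to the right thigh, against the Mexico visit steps and their footnotes; a minor conflict, confined to attribution of local reactions in Mexico

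*Protocol*

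**What the plan says.** **Product section.** Protocol 6.2.2.2, for Prevnar 13: "Each 0.5 mL dose is to be injected IM middle section of lower third of the anterolateral region of the right thigh". The sentence is a flat instruction, without the softening used elsewhere. Section 6.1.1.2 places "MenACYW conjugate vaccine in the thigh (preferably the right thigh". Section 6.1.2.2 sends Menveo to the anterolateral thigh and names no side.

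**Visit steps (Protocol 5.1.4).** For Prevnar 13, Mexico Visit 1 says "inject IM into the anterolateral thigh (preferably the left thigh" and Mexico Visit 2 says "inject IM into the anterolateral area of the thigh (preferably the left thigh". Mexico Visits 3 and 5 and Russian Visit 1 give the same side. The meningococcal vaccine is preferred in the right thigh at every visit where it is given. Russian Visit 3 prefers the right thigh for Prevnar 13, with Pentaxim on the left and no meningococcal vaccine.

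**Footnotes.** At Mexico Visits 1, 2, 3 and 5: "The only other vaccine that can be administered with the meningococcal vaccine in the right thigh is ENGERIX-B". The next sentence of each tells sites not to use the right thigh for Pentaxim or Prevnar 13. Footnote a at Mexico Visit 1, repeated at Russian Visit 1, adds: "Failure to administer vaccines in the designated limb will not constitute a protocol deviation, but should be recorded as a comment in the CRF". It continues: "If the initial vaccines are administered in the wrong limbs, this should be corrected for subsequent injections". Injections in one limb should be "preferably 2.54 cm to 3.81 cm apart with a minimum of 2.54 cm".

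**The concern.** Two parts of the protocol designate different limbs for the same vaccine, and in Mexico the product section points to the limb that the visit footnotes forbid. In Mexico the visit steps in effect reserve one thigh for the meningococcal vaccine; section 6.2.2.2 would remove that separation.

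The separation helps attribution. Under section 9.3.2.3.5, injection-site events count as related to the administered product without an investigator's opinion, so the recorded site carries the attribution. Table 9.1 grades severe tenderness by movement of the whole limb, and Grade 3 erythema or swelling is 50 mm or more. With two injections in one thigh, such reactions could be hard to assign to Prevnar 13 rather than to MenACYW or Menveo. The Group 1 versus Group 2 safety description is a stated observational objective.

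**Working it through.** The plan gives no figure on this point, so there is none to reproduce. The check compares the instructions and then counts planned doses.

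**Prevnar 13 limb by source**

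| Source | Limb | Meningococcal vaccine at that visit? |
|---|---|---|
| 6.2.2.2, all doses | Right | Not considered |
| Mexico Visits 1, 3, 5 | Preferably left; right barred by footnote | Yes, Groups 1 and 2 |
| Mexico Visit 2 | Preferably left; right barred by footnote | Group 2 only |
| Russian Visit 1 | Preferably left | No |
| Russian Visit 3 | Preferably right | No |

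The right-thigh footnote also appears at Russian Visits 2, 4 and 6, but no Prevnar 13 is given then (Table 5.2). Only the four Mexico footnotes conflict with 6.2.2.2 in practice.

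**Inputs.** Planned group sizes are 200, 100, 150 and 75 (section 6.5). Schedules come from Tables 5.1 and 5.2.

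**Formula.** Shared doses = group size × number of visits with both Prevnar 13 and a meningococcal vaccine.

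- Group 1 (months 2, 6, 12): 200 × 3 = 600, of 200 × 4 = 800 Prevnar 13 doses.
- Group 2 (months 2, 4, 6, 12): 100 × 4 = 400, of 100 × 4 = 400.
- Russia: Prevnar 13 at 2 and 4.5 months, 225 × 2 = 450 doses; MenACYW at 3, 6 and 12 months; shared doses = 0.
- Mexico Prevnar 13 total: 800 + 400 = 1,200.

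**Shared-thigh doses in Mexico under each reading**

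- Visit steps followed throughout: 0.
- Section 6 alone (6.2.2.2 with 6.1.1.2): up to 600, or 600/1,200 = 50%. This is Group 1 only, because 6.1.2.2 gives Menveo no side.
- 6.2.2.2 for Prevnar 13, with the visit steps' right-thigh preference for Menveo: up to 600 + 400 = 1,000, or 1,000/1,200 = 83.3%.

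**Comparison.** Under the visit steps' preferred limbs, Prevnar 13 already shares the left thigh with Hexacima at every Mexico vaccination visit: 300 × 4 = 1,200 of 1,200 doses.

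**Spacing.** Grade 3 erythema or swelling against the minimum separation: 50 mm / 25.4 mm = 1.97. A reaction of that size could reach the neighbouring injection point.

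**Route to the analysis sets.** Sections 12.2.4 and 12.2.5 list administration not done as per-protocol among the relevant protocol deviations. Footnote a says a wrong limb is not a deviation, so that exclusion should not be triggered by limb choice.

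**The case against.** The case for leaving this alone is that a site working from the Mexico visit procedures has a clear answer: left at every visit, with an express bar on the right. The visit steps also defer to Operating Guidelines, which are not available here. Safety is descriptive, sharing a thigh is already planned for Prevnar 13 and Hexacima, and erythema is defined as including the needle entry point, which helps assign it. At Mexico Visits 1, 3 and 5 both groups receive a meningococcal vaccine with Prevnar 13, so any blurring could arise in both arms; only Visit 2 differs.

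All of that stands, and it limits the consequence. It does not reconcile the text: 6.2.2.2 is an operative instruction that breaks the footnotes if followed.

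A reader might infer more than the documents support:

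- *That section 6 alone directs 1,000 shared doses.* It does not; the 400 Group 2 doses require a site to take Menveo's side from the visit steps while ignoring the same steps for Prevnar 13.
- *That sites cannot tell which limb to correct to.* The visit steps tell them, and the footnote says later injections should, not must, be corrected.
- *That Russian Visit 3 is a further error.* No meningococcal vaccine is given then, and each vaccine has its own limb.
- *That the primary results are at risk.* Footnote a closes the route to per-protocol exclusion.

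**Conclusion.** The contradiction is real and its consequence is minor. Section 6.2.2.2 conflicts with the preferred limb at all four Mexico vaccination visits and at Russian Visit 1, and with the four Mexico footnotes.

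The exposure runs from 0 to 600 Group 1 doses on section 6 alone, and to 1,000 of 1,200 Mexico doses only under the mixed reading. In Russia it is 0. These are ceilings: they assume planned enrolment, every dose given, every Prevnar 13 dose following 6.2.2.2 and every meningococcal dose going to the right thigh. The limb actually used is unknown.

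What could be affected is attribution of limb-level tenderness or large local reactions between Prevnar 13 and the meningococcal vaccine in the descriptive Mexico safety results. The hSBA endpoints and the per-protocol sets are unaffected.

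**What to change.** In section 6.2.2.2, keep the anatomical description and change only the limb. Replace the reference to the right thigh with: 'of the thigh, preferably the left; not the thigh used for the meningococcal vaccine at that visit'. Add that Russian Visit 3 is an exception, with the right thigh preferred because no meningococcal vaccine is given then. The cost is one corrected line and a short note.

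Optional: if vaccination is complete (the planned vaccination period ended on 14 December 2021) and limb was captured in the database, report by group how many Mexico Prevnar 13 doses shared a thigh with the meningococcal vaccine, beside the injection-site results in the clinical study report. The protocol asks for the injection site to be documented but does not show limb as a database field. The only case report form entry it describes is a comment when the wrong limb is used. If limb was not captured as a field, the count would need source documents, and the size of the issue does not clearly justify that effort.
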